8.1 Adverse Events

An AE is any untoward medical occurrence in a volunteer, which may occur during or after administration of an Investigational Medicinal Product (IMP) and does not necessarily have a causal relationship with the intervention. An AE can therefore be any unfavourable and unintended sign (including an abnormal laboratory finding), symptom or disease temporally associated with the study intervention, whether or not considered related to the study intervention.

Each adverse event will be graded according to the table for grading severity of adverse events (see **Section 8.9**). The following guidelines will be used to determine whether or not an adverse event is recorded in the study database. Solicited adverse event (*i.e.*, reactogenicity parameters) between day 2 and day 6 after vaccination will be recorded by a study field worker or nurse during daily home visits. Volunteers will be encouraged to attend the study clinic in case of any illness. After Study Day 28, only SAEs, as defined in section 8.4 or new chronic medical conditions that require ongoing medical management will be recorded through the last study visit.

8.2 Adverse Reaction

An AR is any untoward or unintended response to an IMP. This means that a causal relationship between the IMP and an AE is at least a reasonable possibility, i.e., the relationship cannot be ruled out. All cases judged by the reporting medical Investigator as having a reasonable suspected causal relationship to an IMP (i.e. possibly, probably or definitely related to an IMP) will qualify as adverse reactions.

8.3 Serious Adverse Events

An SAE is an AE that results in any of the following outcomes, whether or not considered related to the study intervention.

- Death
- Life-threatening event (i.e., the volunteer was, in the view of the Investigator, at immediate risk of death from the event that occurred). This does not include an AE that, if it occurred in a more severe form, might have caused death.
- Persistent or significant disability or incapacity (i.e., substantial disruption of one's ability to carry out normal life functions).
- Hospitalisation, regardless of length of stay, even if it is a precautionary measure for continued observation. Hospitalisation (including inpatient or outpatient hospitalisation for an elective procedure) for a pre-existing condition that has not worsened unexpectedly does not constitute a serious AE.
- An important medical event (that may not cause death, be life threatening, or require hospitalisation) that may, based upon appropriate medical judgment, jeopardise the volunteer and/or require medical or surgical intervention to prevent one of the outcomes listed above. Examples of such medical events include allergic reaction requiring intensive treatment in an emergency room or clinic, blood dyscrasias, or convulsions that do not result in inpatient hospitalisation.

• Congenital anomaly or birth defect.

8.4 Serious Adverse Reaction (SAR)

An adverse event (expected or unexpected) that is both serious and, in the opinion of the reporting investigator or Sponsors, believed to be possibly, probably or definitely due to an IMP or any other study treatments, based on the information provided.

8.5 Suspected Unexpected Serious Adverse Reactions (SUSARs)

A SUSAR is a SAE that is unexpected and thought to be possibly, probably or definitely related to an IMP.

8.6 Causality Assessment

For every unsolicited AE, an assessment of the relationship of the event to the administration of the vaccine will be undertaken. An intervention-related AE refers to an AE for which there is a probable or definite relationship to administration of a vaccine. An interpretation of the causal relationship of the intervention to the AE in question will be made, based on the type of event; the relationship of the event to the time of vaccine administration; and the known biology of the vaccine therapy (Table 2).

Table 2: Guidelines for assessing the relationship of vaccine administration to an AE.

No Relationship	No temporal relationship to study product and Alternate aetiology (clinical state, environmental or other interventions); and Does not follow known pattern of response to study product
Possible	Reasonable temporal relationship to study product; or Event not readily produced by clinical state, environmental or other interventions; or Similar pattern of response to that seen with other vaccines
Probable	Reasonable temporal relationship to study product; and Event not readily produced by clinical state, environment, or other interventions or Known pattern of response seen with other vaccines
Definite	Reasonable temporal relationship to study product; and Event not readily produced by clinical state, environment, or other interventions; and Known pattern of response seen with other vaccines

8.7 Reporting Procedures for All Adverse Events

All AEs occurring within the 28 days following vaccination observed by the investigators or reported by the volunteer, whether or not attributed to study medication, will be reported in the CRF. All AEs that result in a volunteer's withdrawal from the study will be followed up until a satisfactory resolution occurs, or until a non-study related causality is assigned (if the volunteer consents to this). Serious adverse events (SAEs) will be collected throughout the entire trial period.

8.7.1 Reporting procedures for Serious Adverse Events

Every SAE occurring throughout the trial must be reported by telephone, email or fax to the Sponsor, local Ethics Committee, LSM and DSMB by the investigators within 24 hours of (s)he being aware of the occurrence, even if the investigator considers that the adverse event is not related to vaccination. The SAE will also be reported to Janssen Vaccines & Prevention B.V. at the same time.

Any relevant information concerning the adverse event that becomes available after the SAE report form has been sent (outcome, precise description of medical history, results of the investigation, copy of hospitalisation report, etc.) will be forwarded to the Sponsor in a timely manner. The anonymity of the participant shall be respected when forwarding this information.

A Trial specific SAE reporting form will be used which will include specific reporting contacts and time lines (for both SAEs and SUSARs), and further instruction for the management of the SAE documentation.

8.7.2 Reporting procedures for SUSARS

Suspected unexpected serious adverse reactions (SUSARs) will be reported by the Sponsor according to national regulatory guidelines and to the vaccine manufacturer, Janssen Vaccines & Prevention B.V. The Sponsor pledges to inform the Authorities of any trial discontinuation and specify the reason for discontinuation.

8.7.3 Development Update Safety Report

A Development Safety Update Report (DSUR) for each vaccine will be submitted by the Sponsor to the UK competent authority, Ethics Committee and Janssen Vaccines & Prevention B.V. on the anniversary of the first approval date from the regulatory authority.

8.7.4 Pregnancy Safety Reporting

Any pregnancy occurring in female trial participants during the clinical trial and the outcome of the pregnancy should be recorded and followed up for congenital abnormality or birth defect, at which point it would fall within the definition of "serious".

8.8 Assessment of severity

The severity of clinical and laboratory adverse events will be assessed according to the scales in Tables 5, 6 and 7 below.

GRADING THE SEVERITY OF ADVERSE EVENTS

Labelling of an AE as severe will be defined by the severity threshold highlighted in each table.

Adverse event	Grade	Definition (in degrees Celsius)
Temperature	0	< 37.6
	1	37.6 - 38.0
	2	38.1 - 39.0
	3 (severe)	> 39.0

Table 3: Grading of fever AE

Adverse event	Grade	Definition
Any symptom	0	Absence or resolution of symptom
	1	Mild; Awareness of symptom but tolerated; transient or mild discomfort; little or no medical intervention required
	2	Moderate: Discomfort enough to cause limitation of usual activity (some assistance may be needed); some medical intervention or therapy required
	3	Severe: Significant interference with daily activity, some assistance usually required; medical intervention/therapy required, hospitalisation possible
Injection Site	0	No reaction

reaction (erythema, induration and	1	>3 to ≤50mm
swelling)	2	>50 to ≤100mm
	3	>100mm

Table 4: Grading of solicited symptom AE's

Observation	Grade 1	Grade 2	Grade 3 (severe)
Oral temperature (C)	37.6 – 38.0	38.1 – 39.0	39.1 or greater
Tachycardia (beats/min)	101-115	116-130	>130
Bradycardia (beats/min)	50-54	40-49	<40
Systolic hyper-tension (mmHg)	141-159	160-179	≥180
Diastolic hyper-tension (mmHg)	91-99	100-109	>110
Systolic hypo-tension (mmHg)	85-89	80-84	<80

Table 5. Grading of visit observations AE's

The following ranges are considered normal physiological ranges and are recorded as Grade 0:

Oral temperature between 35.5 and 37.5°Celsius

Resting heart rate between 55 and 100 beats/minute

Systolic blood pressure between 90 and 140 mmHg

8.9 Procedures to be followed in the event of abnormal findings

Eligibility for enrolment in the trial in terms of laboratory findings will be assessed as detailed in Appendix A and B. Abnormal clinical findings from medical history, examination or blood tests will be assessed as to their clinical significance throughout the trial. Laboratory adverse events will be assessed using the site-specific tables in the TMF. If a test is deemed clinically significant, it may be repeated, to ensure it is not a single occurrence. If a test remains clinically significant, the volunteer will be informed and appropriate medical care arranged as appropriate and with the permission of the volunteer. Decisions to exclude the volunteer from enrolling in the trial or to withdraw a volunteer from the trial will be at the discretion of the Investigator.

8.9.1 Specific Haematologic criteria for further evaluation

If, following vaccination, there is a 3 femtoliter (fL) or greater change in the mean corpuscular volume (MCV); or a change in severity by one or more grades from baseline for platelet count, or two or more grades from baseline for hemoglobin; or a clinical condition suggesting a coagulopathy, then a thorough hematologic and coagulation evaluation will occur to include at least the following:

- targeted physical exam
- fibrinogen
- blood smear reviewed by a hematologist for evidence of microangiopathic hemolysis.

8.10 Data Safety Monitoring Board

A Data Safety Monitoring Board (DSMB) will be appointed by the Sponsor to provide real-time safety oversight. The DSMB will review all adverse event data generated from the clinical trials in Oxford and Senegal. In addition, all SAEs deemed possibly, probably or definitely related to study interventions will be reviewed by the DSMB. The DSMB will be notified within 24 hours of the Investigators' being aware of the occurrence of any SAE in both clinical trials. The DSMB will determine whether to stop the study for safety concerns on the basis of thorough reviews of interim safety data.

RESOLVE_IRESSEF_CTP_v4.0 ©University of Oxford. CONFIDENTIAL

The DSMB will be comprised of a minimum of three (3) members. There will be a minimum of two other independent, appropriately qualified committee members and a statistician, appointed on the basis of their qualifications and experience to serve on a DSMB. Details of the DSMB for this trial can be found in Appendix C.

The DSMB will be complemented by an independent Local Safety Monitor (LSM) at IRESSEF, Dakar, Senegal clinical trial site. All correspondence between the PI and the DSMB will be conveyed by the PI to the trial Sponsor.

The chair of the DSMB may be contacted for advice and independent review by the PI or trial Sponsor in the following situations:

- Following any SAE deemed to be possibly, probably, or definitely related to a study intervention.
- Any other situation where the PI or trial Sponsor feels independent advice or review is important.

8.10.1 Safety Report Review

The safety profile will be assessed on an on-going basis by the Investigators. The DSMB will perform independent external safety reviews at specified time periods during the CT. The UOXF Chief investigator, Principal Investigator, and relevant Investigators (as per the trial delegation log) will also review safety issues and SAEs as they arise.

9. STATISTICS

9.1 Description of statistical methods

Statistics will be reported in the form of percentages, frequencies, geometric mean titres and geometric mean fold rises with 95% confidence intervals, per group and per visit. For geometric mean titres and fold rises, data will be log transformed (base 10), and confidence intervals will be calculated on this log scale, prior to transforming back into the original scale for reporting and interpretation. Confidence intervals for proportions will be calculated using the binomial exact method.

9.2 Safety analysis

Safety analysis will be carried out for all vaccinated participants, regardless of whether or not they complete the study.

- Occurrence of each solicited adverse event within 7-day follow-up period (day of vaccination and 6 subsequent days) after vaccination
- Occurrence of unsolicited adverse events within 28 days (day of vaccination and 27 subsequent days) after vaccination
- Occurrence of serious adverse events within 28 days (day of vaccination and 27 subsequent days) after vaccination and over the whole study duration
- Occurrence of a serious adverse event from vaccination to the end of the study

Solicited and unsolicited AE data will be collected at each clinic visit. It will be collected by home visits, clinical review, clinical examination (including observations) and laboratory results. (See Table 3-5).

Hematological (hemoglobin, WBC and platelets) and biochemical (creatinine and ALT) laboratory values will be presented according to toxicity grading scales and tabulated by group.

SAEs, AEs of special interest and withdrawal due to AE(s)/SAE(s) will be described in detail.

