4.4 Secondary Outcome Measures

Safety

The specific endpoints for safety and reactogenicity will be actively and passively collected data on adverse events. The following parameters will be assessed for both groups:

- Occurrence of solicited local reactogenicity signs and symptoms for 7 days following the vaccination
- Occurrence of solicited systemic reactogenicity signs and symptoms for 7 days following the vaccination
- Occurrence of unsolicited adverse events for 28 days following the vaccination
- Change from baseline for safety laboratory measures
- Occurrence of serious adverse events during the whole study duration

Immunogenicity

- Humoral- Ebola GP specific IgG as measured by ELISA
- Cellular- Ebola GP specific T cell cytokine response measured using ex vivo interferon-γ enzyme-linked immunosorbent spot (ELISPOT)

Ebolavirus specific immunogenicity will be assessed by a variety of immunological assays. The primary immunogenicity outcome measures are ELISA IFN-gamma ELISPOT for T cell responses.

Exploratory outcome measures will include Ebola GP specific T cell cytokine response measured using intracellular staining technique (ICS) and multicolour flow cytometry performed with research samples collected at different study timepoints as well as other immunogenicity assays throughout the study. Antibody function will also be assessed using assays to measure neutralisation ability of antibodies to the Ebola glycoprotein. An evaluation of genetic factors associated with immune responses may also be undertaken. These may include:

- Assays to assess immunological aging, dysregulation and senescence, such as telomere length or expression of
 relevant markers and transcription factors.
- Assays to assess presence or absence of other factors affecting vaccine immunogenicity, such as antibodies against viral pathogens including cytomegalovirus.
- Determination of HLA-type

Both primary and exploratory immunology may involve collaboration with other specialist laboratories, including laboratories outside of Senegal (e.g. Europe and USA). This would involve transfer of serum/plasma and/or peripheral blood mononuclear cells (PBMC), but samples would be anonymised. Volunteers will be consented for this during the process of obtaining informed consent for the study.

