APPENDIX A: Grading of Laboratory Adverse Events

Severity grading criteria for clinically significant laboratory abnormalities; adapted from FDA guidelines (22) using Oxford University Hospitals NHS Trust laboratory reference ranges.

Laboratory Test	Grade 1	Grade 2	Grade 3
Hgb (female) – gm/dL	10.5 – 11.5	9.0 - 10.4	<9.0
Ref range 12.0 – 15.0			
Hgb (male) – gm/dL	11.5 – 12.5	10.0 - 11.4	<10.0
Ref range 13.0 – 17.0			
WBC- elevated (x10*9/L)	11.50 - 15.00	15.01 - 20.00	>20.0
Ref range 4.0-11.0			
WBC- low (x10*9/L)	2.50 - 3.50	1.50 – 2.49	<1.50
Ref range 4.0-11.0			
Neutrophils decrease (x10*9/L)	1.00 - 1.49	0.50 – 0.99	<0.50
Ref range 2.0-7.0			
Lymphocytes decrease (x10*9/L)	0.75 - 1.00	0.50 – 0.74	<0.50
Ref range 1.0-4.0			
Eosinophils (x10*9/L)	0.65 – 1.50	1.51 – 5.00	>5.00
Ref range 0.0-0.5			
Platelets (x10*9/L)	125 – 135	100 - 124	<100
Ref range 150-400			
Bilirubin – when accompanied by any increase in	1.1 – 1.25 x ULN	>1.25 – 1.5 x ULN	>1.5 – 1.75 x
Liver Function Test increase by factor			ULN
Ref range 3-17 (umol/L)			
Bilirubin- when LFTs normal; increase by factor	1.3 – 1.5 x ULN	1.6 – 2.0 x ULN	>2.0 x ULN
Ref range 3-17 (umol/L)			
ALT, AST; increase by factor	1.25 – 2.5 x ULN	>2.5 – 5.0 x ULN	>5.0 x ULN
Ref range 10-45 (IU/L)			
Alkaline phosphate- increase by factor	1.1 – 2.0 x ULN	2.1 – 3.0 x ULN	>3.0 x ULN
Ref range 95-280 (IU/L)			
Albumin- low (g/L)	28 – 31	25 – 27	<25
Ref range 35-50			
Creatinine	1.1–1.5 x ULN	>1.6–3.0 x ULN	>3.0 x ULN
Ref range 54-145 (umol/L)			
Urea (mmol/L)	8.2 – 8.9	9.0 - 11.0	>11.0
Ref range 2.5-6.7			
Sodium- elevated (mmol/L)	146 – 147	148 – 149	≥150
Ref range 135-145			
Sodium- low (mmol/L)	132 – 134	130 – 131	≤129
Ref range 135-145			
Potassium- elevated (mmol/L)	5.1 – 5.2	5.3 – 5.4	≥5.5
Ref range 3.5-5.0			
Potassium- low (mmol/L)	3.2 –3.3	3.0 - 3.1	≤2.9
Ref range 3.5-5.0			

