APPENDIX B: Laboratory Values for exclusion

Laboratory parameters for inclusion/exclusion in the trial will be considered on an individual basis, with investigator discretion for interpretation of results and the need for repeated tests. In general, volunteers will be excluded if a result at screening constitutes what would qualify as a grade 1 (or higher) laboratory adverse event, according to the site-specific laboratory adverse event tables (0). Urinalysis at screening will be assessed as per the table below:

URINE ANALYSIS (using MULTISTIX)		
Protein*	2+ or Protein creatinine ratio of ≥50mg/mmol	
Blood [£]	2+ on two dipstick tests	
Glucose	1+	

*In the event of the dipstick testing positive for protein with \geq 1+ protein urine should be sent for a protein creatinine ratio.

^{*f*} In the event of urine dipstick testing positive for $\geq 1 +$ blood with, or without, protein in volunteers a repeat dipstick test will be carried out to confirm haematuria. In female volunteers, a menstrual history will be taken to elicit whether the participant is currently menstruating and if they are, urine dipstick will be repeated after 1 - 2 weeks. If blood and/or proteinuria persist in any volunteer, they will be excluded from the trial, and the appropriate follow-up arranged.

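### Section 4.4 makes laboratory change from baseline a secondary outcome, but section 9.2 plans only a toxicity-grade table, with no paired change or grade shift

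*Protocol*

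**What the plan says.** Section 4.4 (Secondary Outcome Measures, Safety) lists "Change from baseline for safety laboratory measures".

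Section 9.2 is the only place in the protocol that says how laboratory data will be analysed. It names haemoglobin, WBC, platelets, creatinine and ALT, and states that the "laboratory values will be presented according to toxicity grading scales and tabulated by group". Section 9.1 gives the general reporting rule, to be applied to each group at each visit: "Statistics will be reported in the form of percentages, frequencies, geometric mean titres and geometric mean fold rises with 95% confidence intervals". None of these is a summary of change in a laboratory value.

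On entry, Appendix B says "In general, volunteers will be excluded if a result at screening constitutes what would qualify as a grade 1 (or higher) laboratory adverse event", and that laboratory parameters "will be considered on an individual basis, with investigator discretion for interpretation of results".

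The only grading scale shown is Appendix A, which sets absolute cut-offs or multiples of the upper limit of normal. For male haemoglobin the row reads "Hgb (male) – gm/dL 11.5 – 12.5 10.0 - 11.4 <10.0" (Grades 1, 2 and 3). Sections 7.5.1 and 8.9 assign grading after enrolment to site-specific tables in the trial master file, and Appendix B refers to site-specific tables for the screening exclusion as well. Those tables are not part of the protocol.

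**The concern.** The outcome in 4.4 and the presentation in 9.2 are different quantities. A change from baseline uses each participant's own earlier value. A toxicity grade on a scale like Appendix A uses only the current value and a fixed line. An analysis that follows 9.2 as written would give counts of grades and no change.

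This matters more here than in a controlled trial. Everyone receives the same vaccine, about 20 people are expected, and each person's pre-vaccination value is the natural comparator for laboratory data. Three things are at stake:

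- A shift shared by many participants but too small to cross a cut-off is not displayed.
- A trivial change next to a cut-off is displayed as an event.
- A participant admitted at Grade 1 by discretion appears as a graded case after vaccination, with nothing in the table to show that the abnormality was there before.

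**Working it through.** The protocol gives no calculated figure for this outcome, so there is none to reproduce. The check has three parts.

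**1. What can stay at Grade 0 on Appendix A (illustrative, since the site tables govern).** The last ungraded value lies just beyond the Grade 1 limit: 12.6 g/dL for male haemoglobin (Grade 1 starts at 12.5), 11.6 for female haemoglobin (11.5), 136 x 10^9/L for platelets (135), and just under 1.25 x 45 = 56.25 IU/L for ALT.

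| Measure | Before | After | Change | Grade |
|---|---|---|---|---|
| Hb, male (g/dL) | 16.5 | 12.6 | -3.9 (-24%) | 0 to 0 |
| Hb, male, top of range | 17.0 | 12.6 | -4.4 (-26%) | 0 to 0 |
| Platelets (x 10^9/L) | 300 | 136 | -164 (-55%) | 0 to 0 |
| Platelets, top of range | 400 | 136 | -264 (-66%) | 0 to 0 |
| ALT (IU/L), bottom of range | 10 | just under 56.25 | 5.6-fold | 0 to 0 |
| Hb, female (g/dL) | 11.6 | 11.5 | -0.1 | 0 to 1 |

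The rows marked top or bottom of range are upper bounds. From the other end of the reference range little goes unscored: male haemoglobin 13.0 to 12.6 is -0.4 g/dL, and platelets 150 to 136 is -9%. The grade therefore depends heavily on where a person started.

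**2. Size at group level.** Assumptions, none of them in the protocol: all male, mean haemoglobin 15 g/dL before vaccination, SD 1.0 (the reference range 13.0 to 17.0 divided by 4), a common true fall d, n = 20. With cut-off 12.55 to allow for rounding, P(Grade 1 or higher) = Phi((12.55 - (15 - d)) / 1.0).

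- d = 0.5: Phi(-1.95) = 0.026; expected 0.5 of 20; chance of none (1 - p)^20 = 60%.
- d = 1.0: Phi(-1.45) = 0.074; expected 1.5 of 20; chance of none 22%.
- d = 1.5: Phi(-0.95) = 0.171; expected 3.4 of 20; chance of none 2%.

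The 95% CI half-width of the mean paired change is about 1.96 x SD of change / sqrt(20). It is 0.22 g/dL for an SD of change of 0.5, and 0.44 g/dL for an SD of 1.0. A fall of 1.0 g/dL would be plain in the paired summary but would appear as one or two Grade 1 results in the grade table. A fall of 0.5 would more often than not produce no graded result, while the paired interval would exclude zero if the observed mean fall were 0.5 (0.5 against 0.22 or 0.44).

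A simulation that requires Grade 0 at entry points the same way. It takes the Appendix A ranges as the central 95% of true values, half of participants male, and assumed visit-to-visit CVs of 2.5 to 4.5% for haemoglobin and 7 to 11% for platelets. A 20% platelet fall in everyone gives a platelet grade in about 7 to 8% of people. A 5% haemoglobin fall in everyone gives a haemoglobin grade in about 4 to 6%.

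**3. Which laboratory values exist.** The synopsis puts safety bloods on Days 0, 7 and 28. Table 1 enters haematology (2 mL) and biochemistry (4 mL) at screening and Day 7 only. Its daily totals confirm this reading: screening 2 + 2 + 4 = 8 mL (with HIV/HBV), Day 7 30 + 2 + 4 = 36 mL, and Days 0 and 28 30 mL each, which is the immunology sample alone. So the baseline could be screening or Day 0, and there may be one or two follow-up values, depending on which passage is read.

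**The case against.** The strongest reply is that 9.2 nowhere says that grades are the only presentation. Section 4.4 keeps the outcome in force, 9.1 reports per visit, and table layouts usually belong to the SAP, which is not shown and may contain the change summary. The protocol also expresses change in grades elsewhere: section 8.9.1 triggers haematological evaluation on a shift in platelet or haemoglobin grade from baseline. For someone who starts at Grade 0, any later grade is itself a change from baseline.

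Part of this stands. The SAP may repair the gap, and threshold crossings are captured. But the protocol has not left the laboratory method open: it states one, and that method does not yield the outcome named in 4.4. Section 8.9.1 is a trigger for clinical evaluation and does not describe a reported analysis. It also uses a change in MCV on its own scale, which shows that the protocol regards within-person change as informative.

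A reader might be tempted by four stronger readings that the documents do not support.

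- **Everyone starts at Grade 0.** Appendix B says so only in general and allows discretion.
- **A common shift would be reported as no laboratory toxicity.** With the simulated rates, the chance of at least one graded person in 20 is 1 - (1 - p)^20: 75 to 79% for platelets (p = 0.067 to 0.076) and 58 to 73% for haemoglobin (p = 0.042 to 0.063). The shift would be poorly described, but not necessarily invisible.
- **The governing scale has no change criterion.** That is known only of Appendix A, because the site tables are not shown.
- **The unreported changes are vaccine effects.** Without a control group, a before-after change cannot be attributed to the vaccine.

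**Conclusion.** The mismatch between 4.4 and 9.2 is real and rests on the protocol's text alone. As written, the plan names change from baseline as an outcome and specifies a presentation that mainly counts threshold crossings, with neither a paired change nor a baseline-to-post grade shift. Changes short of a cut-off would go unreported, and a Grade 1 result already present at entry could look new.

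The size is known only by illustration. The individual examples rest on Appendix A, and the group figures also rest on assumed means, SDs and CVs. With about 20 people, a mean haemoglobin fall of 1.0 g/dL would give roughly 1.5 graded participants, against a paired interval of about ±0.22 to ±0.44 g/dL. The conclusion that 9.2 needs a change summary does not depend on these figures.

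The point is moderate: the outcome is secondary, the analysis is descriptive, and no stated decision rule uses the table. It should be corrected because the repair is simple and the paired comparison is the most informative use of these data.

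**What to change.** Add to section 9.2:

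> For haemoglobin, WBC, platelets, creatinine and ALT, the within-participant change from the pre-vaccination value to each scheduled post-vaccination value will be summarised with its 95% CI (difference for haemoglobin; ratio on the log scale for the others), and toxicity grades will be tabulated as a shift from the pre-vaccination grade.

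State which sample is the baseline for laboratory values. Reconcile the synopsis with Table 1 on the days when safety bloods are taken, because until then neither the baseline nor the set of follow-up values is fixed. State that the change is descriptive and is not attributed to the vaccine.

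The cost is one sentence and one extra descriptive table. No new samples are needed for the visits already marked in Table 1. Whether other visits carry safety bloods depends on how the two passages are reconciled.
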